8.2 Recording of Adverse Events

At each contact with the subject, the study team must seek information on adverse events by specific questioning and, as appropriate, by examination. Information on all adverse events should be recorded immediately in the source document, and also in the appropriate adverse event section of the case report form (CRF). All clearly related signs, symptoms, and abnormal diagnostic, laboratory or procedure results should be recorded in the source document.

All adverse events occurring during the study period must be recorded. The clinical course of each event should be followed until resolution, stabilization, or until it has been ultimately determined that the study treatment or participation is not the probable cause. Serious adverse events that are still ongoing at the end of the study period must be followed up, to determine the final outcome. Any serious adverse event that occurs after the study period and is considered to be at least possibly related to the study treatment or study participation should be recorded and reported immediately.

8.3 Reporting of Serious Adverse Events and Unanticipated Problems

When an adverse event has been identified, the study team will take appropriate action necessary to protect the study participant. The sponsor-investigator will evaluate the event and determine the necessary follow-up and reporting required.

8.3.1 Sponsor-Investigator reporting: notifying the Mayo IRB

The sponsor-investigator will report to the Mayo IRB any UPIRTSOs and Non-UPIRTSOs according to the Mayo IRB Policy and Procedures.

The sponsor-investigator will review all adverse event reports to determine if specific reports need to be made to the IRB and FDA. The sponsor-investigator will sign and date the adverse event report when it is reviewed. For this protocol, only directly related SAEs/UPIRTSOs will be reported to the IRB.

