8.1 Definitions

Unanticipated Problems Involving Risk to Subjects or Others (UPIRTSO)

Any unanticipated problem or adverse event that meets the following three criteria:

- Serious: Serious problems or events that results in significant harm, (which may be physical, psychological, financial, social, economic, or legal) or increased risk for the subject or others (including individuals who are not research subjects). These include: (1) death; (2) life threatening adverse experience; (3) hospitalization - inpatient, new, or prolonged; (4) disability/incapacity - persistent or significant; (5) birth defect/anomaly; (6) breach of confidentiality and (7) other problems, events, or new information (i.e. publications, DSMB reports, interim findings, product labeling change) that in the opinion of the local investigator may adversely affect the rights, safety, or welfare of the subjects or others, or substantially compromise the research data, **AND**
- Unanticipated: (i.e. unexpected) problems or events are those that are not already described as potential risks in the protocol, consent document, not listed in the Investigator's Brochure, or not part of an underlying disease. A problem or event is "unanticipated" when it was unforeseeable at the time of its occurrence. A problem or event is "unanticipated" when it occurs at an increased frequency or at an increased severity than expected, **AND**
- Related: A problem or event is "related" if it is possibly related to the research procedures.

Adverse Event

An untoward or undesirable experience associated with the use of a medical product (i.e. drug, device, biologic) in a patient or research subject.

Serious Adverse Event

Adverse events are classified as serious or non-serious. Serious problems/events can be well defined and include;

- death
- life threatening adverse experience
- hospitalization
- inpatient, new, or prolonged; disability/incapacity
- persistent or significant birth defect/anomaly

and/or per protocol may be problems/events that in the opinion of the sponsor-investigator may have adversely affected the rights, safety, or welfare of the subjects or others, or substantially compromised the research data.

All adverse events that do not meet any of the criteria for serious, should be regarded as **non-serious adverse events**.

Adverse Event Reporting Period

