8.3.2 Sponsor-Investigator reporting: Notifying the FDA

The sponsor-investigator will report to the FDA all unexpected, serious suspected adverse reactions according to the required Investigational New Drug Application, IND Safety Reporting timelines, formats and requirements.

Unexpected fatal or life threatening suspected adverse reactions where there is evidence to suggest a causal relationship between the study drug/placebo and the adverse event, will be reported as a serious suspected adverse reaction. This will be reported to the FDA on FDA Form 3500A, no later than 7 calendar days after the sponsor-investigator's initial receipt of the information about the event.

Other unexpected serious suspected adverse reactions where there is evidence to suggest a causal relationship between the study drug/placebo and the adverse event, will be reported as a serious suspected adverse reaction. This will be reported to the FDA on FDA Form 3500A, no later than 15 calendar days after the sponsor-investigator's initial receipt of the information about the event.

Any clinically important increase in the rate of serious suspected adverse reactions over those listed in the protocol or product insert will be reported as a serious suspected adverse reaction. This will be reported to the FDA on FDA Form 3500A no later than 15 calendar days after the sponsor-investigator's initial receipt of the information about the event.

Findings from other studies in human or animals that suggest a significant risk in humans exposed to the drug will be reported. This will be reported to the FDA on FDA Form 3500A, no later than 15 calendar days after the sponsor-investigators initial receipt of the information about the event.

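### Section 8.3.1 limits IRB reports to directly related events, contradicting its own opening sentence and the possibly-related threshold in the UPIRTSO definition of 8.1

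*Combined protocol and SAP*

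**What the plan says.** Section 8.1 introduces the UPIRTSO as "Any unanticipated problem or adverse event that meets the following three criteria": serious, unanticipated and related. On the third criterion, an event counts "if it is possibly related to the research procedures". The seriousness criterion reaches beyond drug reactions and includes, for example, a breach of confidentiality.

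Section 8.3.1 then gives two instructions on what goes to the IRB. It opens: "The sponsor-investigator will report to the Mayo IRB any UPIRTSOs and Non-UPIRTSOs according to the Mayo IRB Policy and Procedures". It closes: "For this protocol, only directly related SAEs/UPIRTSOs will be reported to the IRB". The protocol does not say what makes an event directly related.

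Two neighbouring sections bear on the point. Section 8.2 says that a serious adverse event arising after the study period and "considered to be at least possibly related to the study treatment or study participation should be recorded and reported immediately"; it does not say to whom. Section 8.3.2 sets a separate route: "The sponsor-investigator will report to the FDA all unexpected, serious suspected adverse reactions", with 7-day and 15-day limits.

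**The concern.** The closing sentence of 8.3.1 asks for a stronger causal link than the definition of the thing to be reported. It announces itself as specific to this protocol and uses the word only, so a study team could reasonably take it as overriding the general promise two paragraphs earlier.

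At stake is whether the IRB hears of individual events in a study that section 8 rates as above minimal risk and that doses healthy volunteers. Under 8.3 and 8.3.1 the sponsor-investigator judges each event and decides what is reported. Section 5.8 keeps the blind until the data analysis is complete, and no procedure for unblinding a single subject is described, so a direct link to the drug may be hard to assert. The heading of 8.5.1 names an internal board, but its text describes only a monitoring plan, which section 10.1 says is attached to the IRB application and which is not part of these documents.

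**Working it through.** No arithmetic applies: the point depends on no rate, variance or sample size. The check sets the rules side by side and runs test events through them.

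| Place | Covers | Causal link required | Recipient |
|---|---|---|---|
| 8.1, UPIRTSO definition | Serious and unanticipated problems, drug-related or not | Possible | None (a definition) |
| 8.3.1, opening sentence | UPIRTSOs and Non-UPIRTSOs | Nothing beyond the definition | IRB, under its policy |
| 8.3.1, closing sentence | SAEs/UPIRTSOs only | Direct (undefined) | IRB |
| 8.2, last sentence | SAEs after the study period | At least possible | Not named |
| 8.3.2 | Unexpected serious suspected adverse reactions | Suspected; the 7-day and first 15-day categories refer to evidence pointing to the drug or placebo as cause | FDA |

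**Event A: serious, unanticipated, possibly but not directly related.** It is a UPIRTSO under 8.1. The opening sentence of 8.3.1 sends it to the IRB; the closing sentence excludes it. Both cannot be followed.

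**Event B: as A, but tied to a study procedure or to data handling rather than to the capsule.** The result at the IRB is the same. It may also fall outside 8.3.2, which concerns suspected reactions to drug or placebo, so it could reach neither body promptly.

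**Event C: not a UPIRTSO and not serious.** The opening sentence covers it, in whatever manner the IRB policy sets. The closing sentence leaves it out whatever its cause.

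**The other way to parse the closing sentence.** If the adverb qualifies only the SAEs and not the UPIRTSOs, event A is reported and the conflict with 8.1 goes away. The conflict over event C remains, because the sentence still admits nothing but SAEs and UPIRTSOs. On either parse, 8.3.1 disagrees with itself.

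**Weight of 8.2.** Its last sentence uses the lower threshold, but only for events after the study period and without naming the IRB. It supports the lower threshold indirectly; it is not a second direct contradiction.

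**The case against.** The strongest reply is that nothing need be withheld. The opening sentence of 8.3.1 already commits the sponsor-investigator to IRB policy, and a team that follows it will report event A. This stands as far as it goes: the harm is conditional on the closing sentence being followed. The policy is not in the documents, so nobody working from them can say which sentence prevails in practice. That uncertainty is a reason to amend, not to leave the text alone.

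A reader might infer that the rule takes most serious events out of external oversight. The documents do not support that. Section 8.3.2 keeps an FDA route with no directly-related limit, and section 10.2 allows the IRB and government agencies to audit and inspect. What is narrowed is notification of the IRB.

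A reader might also infer that every serious event graded possible or probable would be lost. The protocol contains no such grading scale, and since direct relatedness is undefined, how it would divide events is unknown. The conflict with 8.1 is also confined to unanticipated events: a serious event already described as a potential risk may not be a UPIRTSO at all, unless it is more frequent or more severe than expected.

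Nor do the documents show that a direct link can rarely be established under blinding. Dosing is observed, blood pressure and heart rate are taken every 1-3 minutes, and an event caused by the intravenous line or a stress test can be attributed without breaking the blind. Blinding makes attribution to the drug harder; how often it would be decisive is not known.

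**Conclusion.** Wrong as written. Section 8.3.1 gives two incompatible instructions on IRB reporting, and on its natural reading the second sets a higher causal bar than the protocol's own UPIRTSO definition. Followed literally, it keeps from the IRB events that are serious, unanticipated and possibly but not directly related. The FDA route is a partial backstop, weakest for problems that do not arise from the drug.

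The size cannot be put as a number, because the documents give no expected rate of such events. The finding concerns safety reporting alone: it does not touch the sample size, the primary analysis or the interpretation of the results.

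The self-contradiction in 8.3.1 rests on the wording alone. The conclusion that a UPIRTSO would go unreported also assumes that the adverb qualifies both SAEs and UPIRTSOs and that the team applies the more specific sentence.

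**What to change.** Delete the closing sentence of 8.3.1. The opening sentence and the definition in 8.1 then govern IRB reporting, with one relatedness threshold.

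Keeping the sentence but changing its threshold to at least possibly related would not be enough. It would agree with 8.1, but would still confine reports to SAEs and UPIRTSOs and so still conflict with the opening sentence on Non-UPIRTSOs.

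The cost is one sentence in an amendment and, at most, a few more reports to the IRB. No data collection, randomisation or analysis step changes.

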8.3.2 Sponsor-Investigator reporting: Notifying the FDA

The sponsor-investigator will report to the FDA all unexpected, serious suspected adverse reactions according to the required Investigational New Drug Application, IND Safety Reporting timelines, formats and requirements.

Unexpected fatal or life threatening suspected adverse reactions where there is evidence to suggest a causal relationship between the study drug/placebo and the adverse event, will be reported as a serious suspected adverse reaction. This will be reported to the FDA on FDA Form 3500A, no later than 7 calendar days after the sponsor-investigator's initial receipt of the information about the event.

Other unexpected serious suspected adverse reactions where there is evidence to suggest a causal relationship between the study drug/placebo and the adverse event, will be reported as a serious suspected adverse reaction. This will be reported to the FDA on FDA Form 3500A, no later than 15 calendar days after the sponsor-investigator's initial receipt of the information about the event.

Any clinically important increase in the rate of serious suspected adverse reactions over those listed in the protocol or product insert will be reported as a serious suspected adverse reaction. This will be reported to the FDA on FDA Form 3500A no later than 15 calendar days after the sponsor-investigator's initial receipt of the information about the event.

Findings from other studies in human or animals that suggest a significant risk in humans exposed to the drug will be reported. This will be reported to the FDA on FDA Form 3500A, no later than 15 calendar days after the sponsor-investigators initial receipt of the information about the event.

8.4 Stopping Rules

Subject decision to withdraw from the study; or meeting of any of the exclusion criteria while participating in the study; or emergence of significant subject safety concerns.

8.5 Medical Monitoring

It is the responsibility of the Principal Investigator to oversee the safety of the study at his/her site. This safety monitoring will include careful assessment and appropriate reporting of adverse events as noted above, as well as the construction and implementation of a site data and safety-monitoring plan (see section 10 “Study Monitoring, Auditing, and Inspecting”). Medical monitoring will include a regular assessment of the number and type of serious adverse events.

8.5.1 Internal Data and Safety Monitoring Board

A Data and Safety Monitoring Plan (DSMP) is established to identify and document monitoring activities intended to protect the safety of the subjects, the validity of the data and the integrity of the research study.

9 Data Handling and Record Keeping

9.1 Confidentiality

Information about study subjects will be kept confidential and managed according to the requirements of the Health Insurance Portability and Accountability Act of 1996 (HIPAA).

Those regulations require a signed subject authorization informing the subject of the following:

- What protected health information (PHI) will be collected from subjects in this study
- Who will have access to that information and why
- Who will use or disclose that information
- The rights of a research subject to revoke their authorization for use of their PHI.

In the event that a subject revokes authorization to collect or use PHI, the investigator, by regulation, retains the ability to use all information collected prior to the revocation of subject authorization. For subjects that have revoked authorization to collect or use PHI, attempts should be made to obtain permission to collect at least vital status (long term survival status that the subject is alive) at the end of their scheduled study period.

9.2 Source Documents

Source data is all information, original records of clinical findings, observations, or other activities in a clinical trial necessary for the reconstruction and evaluation of the trial. Source data are contained in source documents. Examples of these original documents, and data records include: hospital records, clinical and office charts, laboratory notes, memoranda, subjects' diaries or evaluation checklists, pharmacy dispensing records, recorded data from automated instruments, copies or transcriptions certified after verification as being accurate and complete, microfiches, photographic negatives, microfilm or magnetic media, x-rays, subject files, and records kept at the pharmacy, at the laboratories, and at medico-technical departments involved in the clinical trial.

9.3 Case Report Forms

Not applicable.

Data Management

Study data will be collected at the source through electronic data streams generated by study devices and using the custom-designed MATLAB (MathWorks, Natick, Massachusetts) routines to extract data from our monitoring systems that we are using in ongoing studies.

Blood samples and urine samples will be stored in the [name] in [name] -86C freezers and batched for analysis.

Data Security and Confidentiality

Patient confidentiality is one of the paramount concerns for Mayo Clinic. Its internal policies for safe guarding the confidentiality of the medical record are some of the most stringent in the health care industry. Institution-wide, it is the expectation that only individuals who need to access specific pieces of confidential data will access such data. Data sheets and other paper records will be kept in locked offices and locked drawers, and properly disposed of after use.

Direct identifiers will be removed from specimens or pieces of data whenever possible, and use of coding and anonymizing will be used where possible. When the results of this study will be made available, the participant's identity will remain confidential. All computers are password protected and there is no access to the LAN, Mainframe, or PC without a password. Password requirements vary by system but all generally use a six-attempt account lockout, passwords of at least six characters which change at least every 180 days with a strict reuse policy and prohibition against shared guest accounts. Individually identifiable or deducible data will not be transmitted by unsecured telecommunications, which include the Internet, email, and electronic File Transfer Protocol (FTP). Further, the data will not be physically moved or transmitted in any way from its location without written approval from appropriate personnel.

Another level of security is conveyed by the fact that the building in which the key personnel are located has limited electronic passkey access during non-business hours i.e., between 6 pm - 6 am and 24 hrs during weekends and national holidays. This facility is also guarded by security personnel who make frequent rounds throughout the building throughout the day. In addition, access to the data centers is severely restricted requiring an electronic passkey or a physical key. Server rooms are further access-controlled through swipe card access.

9.4 Records Retention

The sponsor-investigator will maintain records and essential documents related to the conduct of the study. These will include subject case histories and regulatory documents.

To protect the subjects' confidentiality, subject-specific data and Case Report Forms will be coded. The materials and the subject identification code list will be stored in secure place. Subject names or other directly identifiable information will not appear on any reports, publications, or other disclosures of clinical study outcomes.

The sponsor-investigator will retain the specified records and reports for;

1. Up to 2 years after the marketing application is approved for the drug; or, if a marketing application is not submitted or approved for the drug, until 2 years after shipment and delivery of the drug for investigational use is discontinued and the FDA has been so notified. OR
2. As outlined in the Mayo Clinic Research Policy Manual –“Retention of and Access to Research Data Policy” [REDACTED] whichever is longer

10 Study Monitoring, Auditing, and Inspecting

10.1 Study Monitoring Plan

The investigator will allocate adequate time for such monitoring activities. The Investigator will also ensure that the monitor or other compliance or quality assurance reviewer is given access to all the study-related documents and study related facilities (e.g. pharmacy, diagnostic laboratory, etc.), and has adequate space to conduct the monitoring visit.

A Data and Safety Monitoring Plan (DSMP) is established to identify and document monitoring activities intended to protect the safety of the subjects, the validity of the data and the integrity of the research study. Data and Safety Monitoring Plan was completed and is attached to this IRBe application.

10.2 Auditing and Inspecting

The investigator will permit study-related monitoring, audits, and inspections by the IRB, the sponsor, and government regulatory agencies, of all study related documents (e.g. source documents, regulatory documents, data collection instruments, study data etc.). The investigator will ensure the capability for inspections of applicable study-related facilities (e.g. pharmacy, diagnostic laboratory, etc.).

Participation as an investigator in this study implies acceptance of potential inspection by government regulatory authorities and applicable compliance offices.

11 Ethical Considerations

This study is to be conducted according to United States government regulations and Institutional research policies and procedures.

This protocol and any amendments will be submitted to a properly constituted local Institutional Review Board (IRB), in agreement with local legal prescriptions, for formal approval of the study. The decision of the IRB concerning the conduct of the study will be made in writing to the sponsor-investigator before commencement of this study.

All subjects for this study will be provided a consent form describing this study and providing sufficient information for subjects to make an informed decision about their participation in this study. This consent form will be submitted with the protocol for review and approval by the IRB for the study. The formal consent of a subject, using the Approved IRB consent form, must be obtained before that subject undergoes any study procedure. The consent form must be signed by the subject or the subject's legally authorized representative, and the individual obtaining the informed consent.

12 Study Finances

